# Aims

Our specific aims are to examine: (1) the feasibility, acceptability, and initial efficacy of PNSS-S in a 24-week randomized pilot study; (2) to compare the effect of PNSS-S, relative to SC, on mechanisms thought to underlie smoking abstinence in HIV-positive smokers.

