## Methodology

We will adapt an existing, highly effective PN training program that was developed by Co-I [name] to increase engagement in care within the HIV clinic. The PNs for smoking cessation will be former daily smokers who quit smoking and have remained smoke-free for at least two years. We will train the two PNs, enroll 6 HIV-positive smokers to test the intervention, and finalize our protocol. We will refine the PNSS-S based on feedback from the PNs, the 6 participants, and the study nurse. Next, we will conduct a pilot RCT (N = 72) to test the feasibility, acceptability, and initial efficacy of PNSS-S in a randomized, 2-group, repeated measures design. We will randomize 36 HIV-positive smokers to each condition: PNSS-S or standard care (SC). Assessments will be collected at baseline (BL), and at 4-, 12-, and 24-weeks following BL. We will examine the effect of PN on Quitline contact, quit attempts, adherence to pharmacotherapy, smoking cessation rates, 7-day point prevalence abstinence (with biochemical verification), sustained abstinence, self-efficacy for quitting, social support for smoking cessation, study retention and satisfaction. We will calculate a preliminary effect size estimate of PNSS-S on smoking and other secondary outcomes and mechanisms of change. Data will be used to plan a future full-scale RCT.

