#### **Enrollment**

Once the BL interview is complete, the PI, who is not involved in conducting assessments, will randomize eligible participants to one of two study conditions (PNSS-S or SC). The RA will not be informed of treatment condition assignment. All participants will be scheduled for a week 1 session with an MIC study nurse within one week of the BL appointment. The nurse will use a detailed counseling manual to ensure standardization of treatment delivery.

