## Peer Navigation Social Support for Smoking Cessation Condition (PNSS-S)

Participants in the PNSS-S condition will also meet for a 30-minute session with the study nurse. The nurse will discuss the same content that was provided in the SC condition. In addition (for the PNSS-S condition participants only), the nurse will discuss the importance of social support for guitting and will explain the role of a Peer Navigator (PN). The nurse will then introduce the participant to his/her assigned PN. Finally, the nurse will ask if the participant is ready to set a quit date. Participants who set a quit date will choose the appropriate medication in collaboration with their clinic physician. PNs and nurses will reinforce adherence to the chosen medication. Participants will be informed of the efficacy of pharmacotherapy for smoking cessation. The PN will act as an intermediary between the patient and physician - facilitating the acquisition of the medication by coordinating with the participant's MD for a prescription, reviewing the formulary for medication coverage, ensuring that the prescription is picked up at the pharmacy, and managing any side effects via MD/nurse consultation (similar to their role in improving ART adherence). The PN will also assume the role of providing social support for quitting via weekly phone calls with the participant for 12 weeks. The PN will be well versed with local groups and resources, so that they can direct their participants to the most appropriate services/resources, if the participant is interested. Participants not willing to set a quit date at the time of the nurse visit will be engaged in a discussion of "quitting as a process" and will be encouraged to discuss barriers to quitting. This discussion will continue in contacts with the PN over the coming weeks.

In total, participants randomized to PNSS-S will receive a 30-minute session with the nurse, a quit-day counseling call from the PN (as appropriate), and weekly calls from the PN to address issues based on stage of quit attempt for 12 weeks.

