## Feasibility and Acceptability Measures

Feasibility and acceptability will be assessed using session attendance (recorded as a continuous variable ranging from 1 to 4 study sessions) and retention (coded as a dichotomous

variable with participants who complete the 24-week session characterized as completers and those not attending the final session as non-completers). The Helping Relationships subscale of the Processes of Change Questionnaire will be used to examine satisfaction with PNs in the active condition. CSQ-8 will be used to compare treatment satisfaction by condition.

Efficacy Measures: The main outcome analyses and effect size estimates will be based upon biochemically verified 7-day point-prevalence abstinence at 4-, 12-, and 24-week follow-ups. Pointprevalence abstinence will be verified by saliva cotinine radioimmune assay analysis (cutoff value of < 15 ng/ml) for stated abstinence of 7 days or longer in those not currently using NRT or other nicotinecontaining products. Self-report will always be overridden by objective verification of abstinence in the final analyses. Timeline Followback (TLFB) will be used to assess Quitline contact, enrollment in smokefree.gov, prescription receipt for cessation pharmacotherapy, quit attempts (defined as a 24hour period of no smoking), and continuous abstinence. Breath samples for CO will be obtained at each study visit.

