Treatment Feasibility, Acceptability, & Efficacy. Individual analyses of variance will be conducted to compare treatments (PNSS-S vs. SC) on the continuous variables of number of sessions attended and client satisfaction scores. For treatment retention rate (dichotomous), a chi-square analysis will be used. Analyses will test the hypothesis that PNSS-S improves point prevalence abstinence relative to SC. Tests of the effect of treatment condition on Quitline usage, quit attempts, and on 7-day point-prevalence abstinence across the 4, 12, and 24 week assessments will be conducted using GEE, which provides appropriate modeling of covariance structures when observations are correlated across time. The primary, between groups, independent variable in the GEE analysis is treatment condition assignment, which will be dummy-coded using SC as the reference group.

Following the intention-to-treat principle, all participants who have been randomized will be included in the analyses.

Potential Mechanisms of PNSS-S Effects. Sample size in this trial precludes formal mediation analysis with adequate power. The analyses are designed to test the plausibility of potential mechanisms of the PNSS-S treatment effect. We will examine change in these variables using multilevel modeling as increased social support and self-efficacy for quitting are important outcomes in and of themselves, which may affect long-term smoking outcomes and will be useful in demonstrating the longer-term effects of PNSS-S. Mediators will be examined separately, rather than simultaneously, given our limited sample size. For each mediator, we will fit a multilevel model to obtain both an initial value (intercept) and rate of change (slope) in each of these variables from baseline to week 4. We will first test whether treatment condition predicts change in these variables. We will then enter the intercept and slope parameters from these models into the main GEE model of smoking outcome to determine whether change in these variables predicts smoking outcomes. We will be able to examine whether the effect of treatment is reduced when the mediator is added to the model and can test for significance (not expected given the sample size) using the products of coefficients method. Social support in the 4 weeks after quitting also will be examined as a potential mediator of PNSS-S effects.

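### The only specified Aim 2 test of PNSS-S on social support and self-efficacy stops at week 4, so effects at the end of peer navigator support and at follow-up are not estimated

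*Combined protocol and SAP*

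**What the plan says.** The second aim is "to compare the effect of PNSS-S, relative to SC, on mechanisms thought to underlie smoking abstinence in HIV-positive smokers". The Data Analysis Plan addresses it in the paragraph on potential mechanisms. For each mediator a multilevel model is fitted to "obtain both an initial value (intercept) and rate of change (slope) in each of these variables from baseline to week 4". Two steps follow: "We will first test whether treatment condition predicts change in these variables", and then the analysts will "enter the intercept and slope parameters from these models into the main GEE model of smoking outcome".

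On timing, Methodology states: "Assessments will be collected at baseline (BL), and at 4-, 12-, and 24-weeks following BL". Feasibility and Acceptability Measures agrees with that count, since attendance is "recorded as a continuous variable ranging from 1 to 4 study sessions". Under Enrollment, participants are "scheduled for a week 1 session with an MIC study nurse within one week of the BL appointment". The PNSS-S section has the nurse introduce the PN at that visit, followed by "weekly calls from the PN to address issues based on stage of quit attempt for 12 weeks". Recruitment Procedures likewise has the calls run through study week 12.

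The mechanisms paragraph also treats social support and self-efficacy as worthwhile outcomes in their own right and as informative about effects over the longer term. It adds one further analysis, of social support in the four weeks after quitting, as a possible mediator.

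**The concern.** The analysis window is much shorter than the intervention and the follow-up. The comparison of arms on each mechanism is made after the first few calls, and nothing specified uses the values from the end of PN support or from 12 weeks after it.

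The trial's own logic makes later change plausible. Smokers enter whatever their readiness to quit, and for those who decline a quit date at the nurse visit, the PN is to keep working on barriers in later contacts. The purpose given for examining these variables includes longer-term effects, which a four-week window cannot show.

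At stake is the estimate as well as the test. Methodology promises preliminary effect sizes, including on mechanisms of change, to plan a full-scale trial. As written, the planners would receive a mechanism effect measured early in the intervention, with none at week 12 or week 24.

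A second, narrower issue is that only two scheduled assessments fall in the window. That matters for the person-level intercepts and slopes to be carried into the smoking model.

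**Working it through.** **Figures in the plan.** The plan gives no power, alpha or effect size for Aim 2, so there is no figure to reproduce. Its general remark is that only medium to large effects are likely to reach significance. With 36 per arm, two-sided 5% and 80% power (both assumed), the normal approximation gives a detectable d of (1.96 + 0.84) × √(2/36) = 0.66, which agrees with that remark.

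**Share of the calls delivered by week 4.** The PN is introduced up to one week after baseline, and calls are weekly.
- First call in week 1: 4 calls by week 4, and 4/12 = 33%.
- First call in week 2: 3 calls by week 4, and 3/12 = 25%.

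**Effect of the window on power.** Inputs are 36 per arm (Methodology), two-sided 5% (assumed), no dropout (assumed), and a week-12 effect of d = 0.6 in SDs of the quantity compared (assumed). The share f of that effect present at week 4 is unknown, so it is varied. The calculation is a two-sample t-test on 70 degrees of freedom with noncentrality f × 0.6 × √(36/2).

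| Share present at week 4 | d at week 4 | Power |
|---|---|---|
| one quarter | 0.15 | 10% |
| one third | 0.20 | 13% |
| half | 0.30 | 24% |
| three quarters | 0.45 | 47% |
| all | 0.60 | 71% |

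A second set of assumptions gives the same picture. Take a week-12 effect of 0.5 SD of the score, analysed as a change score with SD √(2(1 − ρ)), and ρ = 0.3, 0.5 or 0.7. By the normal approximation:
- full effect (week 12): 43%, 56% and 78%;
- one third present at week 4: 9%, 11% and 15%;
- one quarter present at week 4: 7%, 8% and 10%.

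**What two measurements identify.**
- *Mean effect.* The terms are intercept, condition, time and condition-by-time. Two arms at two times give four cell means for four coefficients (design rank 4 of 4), so the effect is identified. In a simulated data set, a random-intercept model gave 0.317 (SE 0.197), identical to the difference in mean change.
- *Person-level slopes.* A random intercept and slope with residual error has four variance parameters: intercept variance a, covariance c, slope variance b and residual variance s. With time coded 0 and 1, two measurements supply three moments: Var(y0) = a + s, Cov(y0, y1) = a + c, and Var(y1) = a + 2c + b + s. Two different parameter sets give the same moments:
  - a = 0.7, c = −0.1, b = 0.4, s = 0.3 gives 1.0, 0.6 and 0.7 − 0.2 + 0.4 + 0.3 = 1.2;
  - a = 0.9, c = −0.3, b = 0.8, s = 0.1 gives 1.0, 0.6 and 0.9 − 0.6 + 0.8 + 0.1 = 1.2.
- *Consequence.* The predicted slope weights deviations from the means by (c, c + b) times the inverse covariance matrix, whose determinant is 1.2 − 0.36 = 0.84. The first set gives weights (−0.12 − 0.18)/0.84 = −0.36 on baseline and (0.06 + 0.30)/0.84 = 0.43 on week 4. The second gives (−0.36 − 0.30)/0.84 = −0.79 and (0.18 + 0.50)/0.84 = 0.81. The data cannot choose between them.
- *More visits.* Three assessments give 6 moments and four give 10. In both cases the four parameters have full rank.

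**The case against.** **The Aim 2 test is estimable.** A reader might infer from the two-measurement problem that the Aim 2 comparison cannot be fitted. The documents do not support that. The comparison is a condition-by-time effect, which two measurements identify, and the plan does not write out a random-effects structure. The difficulty belongs to the later step of carrying person-level values into the GEE.

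**The 10% to 13% is one scenario.** A reader might also take it as the power of the planned test. Neither d = 0.6 nor growth in proportion to calls is in the documents. Counting calls may understate early exposure: by week 4 a PNSS-S participant has also had the nurse's discussion of social support, and may have had a quit-day call, help in obtaining medication, and calls of their own to the PN. Support could even peak early, and with the full effect present at week 4 power is 71%.

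**The paragraph is broader than one window.** Its opening statement about examining change has no week-4 limit, and social support after quitting is examined too. Both are true. The opening statement specifies no model, however, and the post-quit analysis is of a mediator and does not test condition.

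**An early window suits mediation.** It places mediator change before abstinence at weeks 12 and 24. This stands in part: the GEE outcome also includes week-4 abstinence, which is concurrent with the week-4 mediator. It does not justify leaving the later visits out of the comparison of arms.

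**This is an exploratory pilot.** The plan puts effect sizes ahead of significance and says formal mediation is underpowered. That reduces the weight of the power figures. It does not supply the missing effect sizes at weeks 12 and 24.

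**The measure-by-visit schedule is in an attachment not supplied.** The count of two measurements, and the availability of later ones, are read from the visit schedule and need confirming.

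**Conclusion.** The concern holds in a limited form. The only specified test of condition on social support and self-efficacy covers baseline to week 4, after about 25% to 33% of the PN calls, and no named model uses week-12 or week-24 values. Followed as written, the plan yields no Aim 2 estimate at the end of PN support and none of persistence. That conclusion needs no assumption about effect size.

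The cost in power does need one. It ranges from severe (10% to 13%, against 71%) if the effect builds in proportion to calls, to none if it is complete by week 4. Even in the latter case persistence is not estimated.

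The identification problem is confined to separating person-level intercepts and slopes from residual error, and rests on two measurements per person at the scheduled times. The mean treatment effect on change is unaffected.

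This should be changed before analysis, as a specification gap in a secondary aim. It does not invalidate the trial.

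**What to change.** - **Aim 2 comparison.** Fit each mechanism with a multilevel model over baseline and weeks 4, 12 and 24, with condition-by-visit terms. Name week 12 (end of PN support) as the main contrast and week 24 as persistence, and report each effect size with a confidence interval.
- **Exploratory mediation.** Keep early change for this step only. Enter the week-4 score with the baseline score as covariate in place of a multilevel intercept and slope. This uses the same two measurements without needing an unidentified variance split.
- **Forms.** Confirm from the Schedule of Assessments that the support and self-efficacy questionnaires are given at weeks 12 and 24.

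The cost is a change of wording in the analysis plan. No visits are added, and no forms either if the questionnaires are already in the later packets. The downside is a few more contrasts per mechanism in an exploratory aim, which naming week 12 in advance keeps in order.

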#### Data Analysis Plan

Assessments will be designed as scannable forms for use with the Cardiff Teleform Scanner System®. Data will be verified, checked, and uploaded to an SPSS file to conduct analyses. Initial data analysis will include studies of randomization effects (group differences), distribution properties of dependent and other variables, and correlations among outcome measures.

Sample Size and Power Considerations. Our primary objective will be to examine preliminary effect sizes for PNSS-S, rather than to determine statistical significance between groups at certain p values. At the same time, we are well aware of the dangers of relying exclusively on small-scale pilots to determine the promise of novel treatment approaches. These effect size estimates have a large standard error, and we primarily will be hoping to find a pattern of results that is supportive of the experimental treatment. Effect size estimates will include odds ratios for smoking abstinence. We believe a sample size of 72 should allow adequate examination of PNSS-S intervention effect sizes while staying within the scope of a developmental project. We recognize that only medium to large effect sizes will be likely to attain statistical significance with a sample of this size. Our data also will allow us to obtain stability estimates for point-prevalence abstinence (i.e., intercorrelations among outcomes at 4, 12, and 24 weeks). Using a program that allows us to specify proportions at each time point and the correlations between time points, we will be able to get a good estimate of the sample size needed to find a significant main effect of treatment in a repeated measures analysis using generalized estimating equations. All analyses will include sex as a covariate and follow-up analyses will test the Sex x Condition interaction to determine whether sex moderates the effects.

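### The aim-2 test of PNSS-S on social support and self-efficacy specifies neither baseline adjustment nor equal baseline means; fitted in the ordinary way, it is a change-score comparison that gives up precision

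*Combined protocol and SAP*

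**What the plan says.** The second specific aim (Aims) is "to compare the effect of PNSS-S, relative to SC, on mechanisms thought to underlie smoking abstinence in HIV-positive smokers". The analysis serving it is in the Data Analysis Plan, under Potential Mechanisms of PNSS-S Effects. Each mediator gets its own multilevel model, which yields an initial value and a rate of change "in each of these variables from baseline to week 4". The test of condition follows: "We will first test whether treatment condition predicts change in these variables". The initial value is used only in the next step: "We will then enter the intercept and slope parameters from these models into the main GEE model of smoking outcome".

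The Methodology section gives the visit times: "Assessments will be collected at baseline (BL), and at 4-, 12-, and 24-weeks following BL". Under Sample Size and Power Considerations, the one covariate named across the board is sex: "All analyses will include sex as a covariate".

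The Data Analysis Plan opens with a look at group differences after randomisation, but states no adjustment that would follow from it. The Enrollment section describes randomisation after the baseline interview and mentions no stratification on these scores.

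**The concern.** The plan regards social support and self-efficacy as outcomes that matter in their own right. The Methodology section lists effect sizes on mechanisms among the results to be carried into planning a full trial. The size and precision of these estimates are therefore part of what the pilot is meant to deliver.

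A change score corrects for baseline with a fixed coefficient of 1. The data would generally support a different coefficient: the correlation times the ratio of the week-4 SD to the baseline SD. Where that is below 1, the change score over-corrects. An arm that happens to start low then tends to show a larger gain through regression to the mean. The interval is also wider than the same data allow. The baseline scores that would avoid both problems are already collected.

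**Working it through.** **Inputs from the documents.** 36 participants per arm and assessments at baseline and weeks 4, 12 and 24 (Methodology); slope window from baseline to week 4, and sex as the covariate (Data Analysis Plan).

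**Inputs assumed.** The plan gives no SD, effect size, significance level or baseline-to-week-4 correlation (rho) for these measures, so it has no figure to reproduce. I take rho from 0.3 to 0.8, two-sided 5% and, for power only, an effect of 0.5 SD. As a consistency check, the effect detectable with 80% power on an unadjusted score with SD 1 is (1.96 + 0.84) × √(2/36) = 0.66 SD. This agrees with the plan's remark that only medium to large effects are likely to reach significance.

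**Step 1: what the test reduces to.** With two measurements, a person's slope is week 4 minus baseline, divided by time. With complete data and a condition effect allowed at baseline, the condition-by-time term equals the difference in mean change. In one simulated data set (rho 0.5, 36 per arm), both routes gave 0.6908.

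**Step 2: variance per person.** Let SD0 and SD4 be the baseline and week-4 SDs.

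- Change score: SD0² + SD4² − 2·rho·SD0·SD4
- Baseline-adjusted: SD4²·(1 − rho²)
- Difference: (SD0 − rho·SD4)², which is never negative

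**Step 3: equal SDs, set to 1.** The variances become 2(1 − rho) and 1 − rho², so adjustment cuts the variance by (1 − rho)/2. The SE is √(variance × 2/36). Power uses the noncentral t distribution with 69 and 68 degrees of freedom.

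| rho | Variance, change | Variance, adjusted | Cut | SE, change | SE, adjusted | Power at 0.5 SD, change vs adjusted |
|---|---|---|---|---|---|---|
| 0.3 | 1.40 | 0.91 | 35% | 0.279 | 0.225 | 42% vs 59% |
| 0.5 | 1.00 | 0.75 | 25% | 0.236 | 0.204 | 55% vs 68% |
| 0.7 | 0.60 | 0.51 | 15% | 0.183 | 0.168 | 77% vs 83% |
| 0.8 | 0.40 | 0.36 | 10% | 0.149 | 0.141 | 91% vs 94% |

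At rho 0.5 the 95% CI half-width (t multiplier about 2.0) falls from 0.47 to 0.41 SD. In 20,000 simulated trials per value, the ratio of change-score to adjusted variance was 1.52, 1.32 and 1.15 at rho 0.3, 0.5 and 0.7. The formula 2/(1 + rho) gives 1.54, 1.33 and 1.18.

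**Step 4: unequal SDs (SD0 = 1).**

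- rho 0.6, SD4 1.25: change 1 + 1.5625 − 1.5 = 1.0625; adjusted 1.5625 × 0.64 = 1.00; cut about 6%.
- rho 0.7, SD4 1.4: change 1 + 1.96 − 1.96 = 1.00; excess (1 − 0.98)² = 0.0004; cut essentially zero.
- rho 0.5, SD4 0.8: change 1 + 0.64 − 0.80 = 0.84; adjusted 0.64 × 0.75 = 0.48; cut about 43%.

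**Step 5: chance imbalance, equal SDs.** One SE of the baseline difference is √(2/36) = 0.236 SD. The change-score estimate moves by (1 − rho) times this, in the opposite direction: 0.17, 0.12, 0.07 and 0.05 SD at rho 0.3, 0.5, 0.7 and 0.8. In the simulations, the slope of the change-score estimate on the imbalance was −0.70, −0.51 and −0.30 at rho 0.3, 0.5 and 0.7; for the adjusted estimate it was about 0. Both estimators averaged 0.50, the true value.

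**Step 6: the other reading of the text.** If condition enters only the slope equation, baseline means are equal by construction. In the data set of step 1 this gave 0.617 (SE 0.188), close to 0.611 from regressing week 4 on condition and baseline. The unconstrained model gave 0.691 (SE 0.221).

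**The case against.** The strongest reply is that the plan does not exclude adjustment. It never says that condition also enters at the intercept, and step 6 shows that a slope-only condition term recovers nearly the whole gain. This stands. A reader might infer that the plan commits to an unadjusted change score, but the text supports only that neither adjustment nor constraint is specified. Two analysts following it could report 0.691 or 0.617 from the same data, which is itself a reason to settle the term.

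Second, the size rests on assumptions. This also stands. The gain depends on the SD ratio as well as on rho, and unequal SDs are plausible because PNSS-S participants are told to count peer navigator support, which they cannot have at baseline. A single headline loss such as 25% is not supported; only the direction is general.

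Third, the stakes are modest. The plan puts effect sizes ahead of significance, admits large standard errors and treats the mechanism analyses as checks of plausibility. Its sample-size planning for the next trial rests on abstinence proportions and their correlations. Power is therefore a secondary yardstick. Precision of effect sizes still matters, because they are the stated product.

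Fourth, the plan first mentions multilevel modelling of these variables without limiting it to week 4, and the Schedule of Assessments is not shown. An additional measurement inside the window would break the exact equality with a change score, but the Methodology and Follow-up Visits sections indicate none.

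A reader might also infer that the aim-2 estimates would be biased. They would not: over repeated randomisations both estimators are unbiased, and the imbalance effect is conditional on the allocation obtained.

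**Conclusion.** The point holds as an omission in the specification. On the ordinary reading, the aim-2 comparison is a difference in mean change, and nothing in the documents supplies a baseline covariate or an equal-means constraint.

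Apart from one degree of freedom, adjustment cannot lose precision. For equal SDs and rho between 0.3 and 0.8, the variance cut is 35% down to 10%. It may be near zero if scores spread out by week 4, and larger if they narrow. A one-SE chance imbalance displaces the change-score estimate by about 0.12 SD at rho 0.5 with equal SDs. All these sizes rest on assumed correlations and SD ratios.

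This is a worthwhile precision improvement to an exploratory estimate. It gives no ground for doubting the abstinence analysis, which it does not touch.

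**What to change.** Under Potential Mechanisms of PNSS-S Effects, state that the effect of condition on social support and on self-efficacy is estimated from a multilevel model with baseline and follow-up scores as outcomes, baseline means constrained equal across arms (no condition term at baseline), and sex as a covariate. Leave the covariance between visits unrestricted so that the two SDs may differ. Report the adjusted mean difference with its 95% CI as the aim-2 effect size for each measure, and use the same form at any later visit analysed.

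This model keeps every randomised participant with any score. Regressing the week-4 score on condition, baseline score and sex gives essentially the same answer with complete data, but needs imputation where week-4 scores are missing. The intercept and slope can still be carried into the exploratory GEE step.

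The cost is one sentence in the plan and at most one degree of freedom. It needs no new data, visits or staff.

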The primary objective of this project is to examine the feasibility, acceptability and initial efficacy of a peer navigation social support for smoking cessation (PNSS-S) intervention for HIV-positive smokers. We will enroll 78 HIV-positive smokers, regardless of their readiness to quit, into a 24-week randomized pilot study to determine whether enhanced treatment (using a PN to navigate smoking cessation, help obtain medication and treatment, improve adherence to treatment, and provide social support for quitting) will increase quit attempts and smoking cessation rates (measured by 7-day point prevalence) compared with standard care (SC; provider recommendation to quit and quit line referral using the 5A's).

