## **Baseline Measures of Individual Differences**

Demographics will include age, sex, gender, race, ethnicity, marital status, employment status, income, education level, number of years living with HIV, and history of opportunistic infections. We will obtain most recent CD4 T-cell value and HIV viral load from the MIC medical record (commonly measured in the clinic every 3-6 months). The Fagerström Test for Cigarette Dependence (FTCD) will be administered to evaluate severity of cigarette dependence. An exhaled carbon monoxide (CO) level will be obtained (using a Smokerlyzer ED50 CO meter [Bedfont Scientific, Haddonfield, NJ]), a valid assessment of recent smoking. Participants will provide breath samples for CO at baseline, and each study interview; values of 5 ppm or higher will be considered indicative of smoking. Intention to quit smoking will be assessed using the Smoking Stage of Change questionnaire. Depressive symptoms will be assessed with the Center for Epidemiologic Studies –Depression scale (CES-D).

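### The step from mediator change to abstinence does not adjust for baseline readiness or dependence, although both are measured, so a mediator with no effect could appear to predict quitting

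*Combined protocol and SAP*

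**What the plan says.** The paragraph on potential mechanisms in the Data Analysis Plan takes each mediator separately. A multilevel model gives the mediator's intercept and its slope from baseline to week 4, and condition is tested as a predictor of change. Next: "We will then enter the intercept and slope parameters from these models into the main GEE model of smoking outcome", the stated purpose being "to determine whether change in these variables predicts smoking outcomes". The plan then looks at whether the treatment effect shrinks once the mediator is in the model, and allows a product-of-coefficients test that it does not expect to be significant.

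On what else is in that model, the plan says: "The primary, between groups, independent variable in the GEE analysis is treatment condition assignment". The paragraph on sample size and power adds: "All analyses will include sex as a covariate". No other covariate is named.

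Under Baseline Measures of Individual Differences, two relevant variables are collected: "Intention to quit smoking will be assessed using the Smoking Stage of Change questionnaire", and "The Fagerström Test for Cigarette Dependence (FTCD) will be administered to evaluate severity of cigarette dependence". Readiness is not restricted at entry (Description and Purpose of the Project): "We will enroll 78 HIV-positive smokers, regardless of their readiness to quit". Of these, 72 are randomised, 36 to each arm.

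The plan warns that formal mediation analysis would be underpowered and limits its aim to plausibility. It says nothing about confounding of the mediator-outcome association.

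**The concern.** Randomisation protects the comparison of arms and the effect of condition on the mediator. It does not protect the association between mediator change and abstinence, because nobody is randomised to a level of support or self-efficacy. Within either arm, readier or less dependent smokers may both gain more confidence or support and quit more often. The slope then carries their advantage even if the mediator does nothing. The attenuation check and the product of coefficients use the same path and inherit the same error.

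Mechanisms are the second specific aim, and the Methodology section says the data will be used to plan a full-scale trial. A confounded association could therefore be read as support for a mechanism. The problem is separate from when the mediator is measured and would remain if abstinence were assessed later.

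**Working it through.** **No figure to reproduce.** The documents give no abstinence rates, no correlations between mediators and baseline factors, and no inputs for the sample of 72. Every strength below is an assumption.

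**Terms in the model.** Planned: condition, sex, mediator intercept, mediator slope. Measured at baseline but absent: Smoking Stage of Change and FTCD.

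**Approximate size.** Let R be a baseline factor, I the mediator intercept and S its slope, each with SD 1. R correlates k with both I and S, and I and S are related only through R, so their correlation is k². R has log-odds g per SD on abstinence, and S has no effect. The coefficient of S when R is regressed on S and I is (k − k³)/(1 − k⁴) = k/(1 + k²). The false log-odds per SD of slope is therefore about g × k/(1 + k²). Without I in the model it would be about g × k.

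| k | g | g × k/(1 + k²) | Approximate false OR | Fitted, with I and condition | Fitted, S alone |
|---|---|---|---|---|---|
| 0.3 | 0.5 | 0.15/1.09 = 0.138 | 1.15 | 1.14 | 1.16 |
| 0.4 | 0.7 | 0.28/1.16 = 0.241 | 1.27 | 1.26 | 1.30 |
| 0.5 | 0.9 | 0.45/1.25 = 0.360 | 1.43 | 1.41 | 1.52 |

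The fitted columns are logistic regressions on 1,000,000 simulated people with 12% abstinent; repeat runs agreed to about 0.01. Adding R returns the odds ratio to 1.00, but that holds by construction, because R is the only confounder simulated.

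**At the planned size.** A second simulation used 72 people, three visits and an exchangeable logistic GEE with condition, sex, intercept and slope. Readiness and dependence each had log-odds of 0.7 per SD in size, abstinence was roughly 20%, and there were 500 runs per setting. The true effect of the slope was nil.

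| Correlation of each factor with I and S | OR per SD of slope, planned model | Nominal 5% test rejects, planned model | Same, readiness and dependence added |
|---|---|---|---|
| 0 | 1.00 | 6% | 9% |
| 0.2 | 1.23 | 14% | 6% |
| 0.3 | 1.34 | 28% | 7% |
| 0.4 | 1.41 | 35% | 7% |

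With both added, the odds ratio was 0.97 to 1.01 throughout.

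**Can the data carry two more terms?** Expected abstainers per visit, at assumed rates in the two arms:
- 5% and 10%: 36 × 0.05 + 36 × 0.10 = 5.4
- 5% and 20%: 36 × 0.05 + 36 × 0.20 = 9.0
- 10% and 25%: 36 × 0.10 + 36 × 0.25 = 12.6

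That is few. A penalised single-visit fit with 72 people and about 10 abstainers still brought the odds ratio back to about 1.0 to 1.03, with a standard error roughly 10 to 20% larger.

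**Effect on the attenuation check.** With no mediator in the model, adding the baseline factor alone moved the treatment odds ratio from 1.90–1.98 to about 2.00–2.02. With two factors at log-odds of 0.7 in size, it moved from 1.91 to 2.05, or from 2.74 to 3.05. Odds ratios shift when prognostic covariates enter, whether or not there is mediation.

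**The case against.** **The model is not unadjusted.** A reader might infer that nothing but the mediator is in it. Condition, sex and the mediator's own intercept are included, and the intercept removes part of the bias. The single-term figures of 1.16, 1.30 and 1.52 therefore do not describe the planned model. With the intercept correlated 0.5 with the baseline factor in all three settings, the false odds ratios were 1.12, 1.23 and 1.41. A change-score structure gave 1.28 to 1.59. Bias remains in each case, but its size depends on a structure the documents do not describe.

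**Support is largely assigned.** Peer navigators call weekly for 12 weeks, including participants unwilling to set a quit date, and condition is in the model. This stands in part: for social support, confounding is plausible mainly through support from other people or uptake of calls. It narrows the concern for that mediator and does not answer it for self-efficacy.

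**The step is exploratory.** The plan disclaims power and speaks only of plausibility. A reader might infer that it promises to show how PNSS-S works, or that a false mechanism would certainly reshape the full trial. The text supports neither. Its caveat concerns precision, however, and low power does not remove bias.

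**Adjustment has its own costs.** With few abstainers, two more terms strain the fit. With no confounding, the false-positive rate was 9% adjusted against 6% unadjusted, imprecisely estimated from 500 runs. Adding covariates to the mediator model alone would also spoil the comparison of treatment effects with and without the mediator. Both points stand and shape the fix.

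**Conclusion.** The concern holds as a limited one about an exploratory step. As written, the mediator-outcome model leaves out two baseline variables that are already collected and could influence both mediator change and abstinence. Under the assumed strengths, and with condition and the intercept included, a mediator with no effect would show an odds ratio of roughly 1.14 to 1.41 per SD of slope. That indicates direction and plausible size. It is neither a forecast nor a bound, since none of the strengths is in the documents.

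A reader might infer that the efficacy result is biased too. It is not on this ground, because that comparison rests on randomised condition. A reader might also infer that adjusting for two variables would make the mechanism estimate causal. It would not, because unmeasured common causes could remain.

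**What to change.** In the paragraph on potential mechanisms:

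- Alongside the planned model, fit the mediator-outcome model with baseline Smoking Stage of Change (one ordered score) and FTCD added, and name the penalised or small-sample-corrected estimator to be used.
- Judge any reduction of the treatment effect against a matching model with the same covariates and estimator but no mediator.
- State that the mediator-outcome association is exploratory and may still be confounded after adjustment.
- Leave the primary efficacy GEE unchanged.

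No new data are needed. The cost is a few sentences, one extra reference model, and two more parameters where abstainers are few, with a standard error roughly 10 to 20% larger under the assumed inputs. If the adjusted fit proves unstable, the statement on confounding is still needed and costs nothing.
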